### **7.4.2 Analysis of Secondary Endpoints**

The secondary efficacy endpoints are defined in [Section 2.3.2 Secondary Endpoints].

The primary analysis for the secondary endpoints of mean daily average pain score ( $\geq 30\%$  and 50% reduction from baseline to Week 8 and to EOT) will be carried out with the Fisher's Exact Test. For the Week 8 analysis, subjects with missing data will be classified as non-responders (BOCF) and an additional analysis will use mBOCF. For the EOT analysis, LOCF will be used.

The primary analysis for the change from baseline to Weeks 2, 4 and 8 for the FIQR subscales of Physical Function, Symptoms and Overall Impact will use the same MMRM analysis as described in [Section 7.4.1.1 Primary Analysis]. The primary analysis for the change from baseline to EOT for the FIQR subscales will use an ANCOVA model, with covariates of baseline FIQR subscale score and center. An additional ANCOVA analysis will be conducted at Week 8 with mBOCF for subjects with missing data.

The primary analysis for the PGIC will use the proportional odds model for ordinal data, with model term for treatment group. The analysis will be used to assess PGIC at Weeks 2, 4, 8 and EOT. For subjects with missing data, the analysis at Weeks 2, 4 and 8 will be conducted using imputation of 'No Change' for subjects who discontinue due to lack of efficacy or AEs,

and imputation by LOCF for subjects with missing data at Week 8 for other reasons. An additional analysis at Weeks 2 and 4 will use LOCF.

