**Table 19 Summary of the Analyses for the Secondary Efficacy Variables**

Variable	Imputation	Analysis Set	Analysis Type
Percentage of subjects achieving $\geq 30\%$ (or $\geq 50\%$ ) reduction from baseline to Week 8 in mean daily average pain score assessed by NRS where all subjects with missing Week 8 data are classified as non-responders	BOCF	FAS	Fisher's exact test
Percentage of subjects achieving $\geq 30\%$ (or $\geq 50\%$ ) reduction from baseline to Week 8 in mean daily average pain score assessed by NRS (Sensitivity analysis)	mBOCF c	FAS	Fisher's exact test
Percentage of subjects achieving $\geq 30\%$ (or $\geq 50\%$ ) reduction from baseline to Week 8 in mean daily average pain score assessed by NRS where all subjects with missing Week 8 data are classified as non-responders (Sensitivity analysis)	BOCF	PPS	Fisher's exact test
Table continued on next page			

Variable	Imputation	Analysis Set	Analysis Type
Percentage of subjects achieving $\geq 30\%$ (or $\geq 50\%$ ) reduction from baseline to EOT in mean daily average pain score assessed by NRS	LOCF	FAS	Fisher's exact test
Change from baseline to Week 2, Week 4 and Week 8 for the FIQR function, symptoms and overall impact subscales	None	FAS	MMRM analysis of change from baseline a
Change from baseline to Week 8 for the FIQR function, symptoms and overall impact subscales (Sensitivity analysis)	Discontinuation-reason based multiple imputation b	FAS	MMRM analysis of change from baseline a
Change from baseline to Week 8 for the FIQR function, symptoms and overall impact subscales (Sensitivity analysis)	None	PPS	MMRM analysis of change from baseline a
Change from baseline to Week 8 for the FIQR function, symptoms and overall impact subscales (Sensitivity Analysis)	mBOCF c	FAS	ANCOVA analysis of change from baseline
Change from baseline to EOT for the FIQR function, symptoms and overall subscales	LOCF	FAS	ANCOVA analysis of change from baseline
Overall subject improvement assessed by PGIC at Week 2, Week 4 and Week 8	mBOCF c	FAS	Proportional odds model
Overall subject improvement assessed by PGIC at Week 2 and Week 4 (Sensitivity analysis)	LOCF	FAS	Proportional odds model
Overall subject improvement assessed by PGIC at EOT	LOCF	FAS	Proportional odds model

aMMRM analysis uses data from baseline and change from baseline data at Week 2, Week 4 and Week 8 time points.

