bDiscontinuation-reason based multiple imputation (MI) will use a "Jump to Reference" algorithm (where placebo is the reference group) for subjects who discontinue due to lack of efficacy or AEs and standard regression-based MI for subjects with missing data for other reasons.

cmBOCF is defined as imputation by baseline observation carried forward for subjects who discontinue due to lack of efficacy or AEs, and imputation by LOCF for subjects with missing data at the specific analysis time point for other reasons.

The following secondary binary response endpoints (responder, non-responder; as defined in Section 6.1.2) will be analyzed using the Fisher's exact test for ASP8062 versus placebo:

- Percentage of subjects achieving  $\geq 30\%$  (or  $\geq 50\%$ ) reduction from baseline to Week 8 in mean daily average pain score assessed by NRS where all subjects with missing Week 8 data are classified as non-responders,
- Percentage of subjects achieving  $\geq 30\%$  (or  $\geq 50\%$ ) reduction from baseline to Week 8 in mean daily average pain score assessed by NRS where mBOCF is used to impute a responder status for subjects with missing Week 8 data, and
- Percentage of subjects achieving  $\geq 30\%$  (or  $\geq 50\%$ ) reduction from baseline to EOT in mean daily average pain score assessed by NRS.

Summary statistics will show the number and percentage of subjects who show response for each treatment group, 2-sided 90% CI for the percentage within each treatment group (ASP8062, placebo) calculated using the exact unconditional approach, difference in

percentages, 2-sided 90% CI for ASP8062 versus placebo calculated using the exact unconditional approach, and 1-sided p-value. In addition, the above responder analysis will be repeated in the PPS as a sensitivity analysis of the percentage of subjects achieving  $\geq 30\%$  (or  $\geq 50\%$ ) reduction from baseline to Week 8 in mean daily average pain score assessed by NRS where all subjects with missing Week 8 data are classified as non-responders.

The following secondary endpoints will be analyzed using the MMRM analysis as described in Section 7.4.1.1 for the primary efficacy analysis (however with only analysis time-points Week 2, Week 4 and Week 8 included):

- Change from baseline to Week 2, Week 4 and Week 8 for the FIQR function, symptoms and overall impact subscales (where no explicit imputation is performed).

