For each endpoint, standard summaries of the MMRM analysis results will be provided, as described in Section 7.4.1.1. This will include an overlay plot. In addition, the MMRM analysis will be repeated in the PPS and also in the FAS under the assumption that data is MNAR using decision-reason based multiple imputation as sensitivity analyses of the change from baseline to Week 8 for the FIQR function, symptoms and overall impact subscales.

The following secondary endpoints will be analyzed using ANCOVA, as described in Section 7.4.1.2 for the second sensitivity analysis of the primary endpoint:

- Change from baseline to Week 8 in FIQR function, symptoms and overall impact subscale scores where mBOCF is used for imputation of missing data at Week 8. Modified baseline observation carried forward is defined as imputation by BOCF for subjects who discontinue due to lack of efficacy or AEs, and imputation by LOCF for subjects with missing data at Week 8 for other reasons.
- Change from baseline to EOT in FIQR function, symptoms, and overall impact subscale scores.

For each endpoint, standard summaries of the ANCOVA results, as described in Section 7.4.1.2 will be provided.

The following secondary endpoints will be analyzed using a proportional odds model for ordinal data including treatment group as a factor:

- Overall subject improvement assessed by PGIC at Week 2, Week 4 and Week 8 where mBOCF will be used for subjects with missing data,
- Overall subject improvement assessed by PGIC at Week 2 and Week 4 where LOCF will be used for subjects with missing data, and
- Overall subject improvement assessed by PGIC at EOT.

At each time point, the proportion of subjects in each treatment group achieving each level of response (1 = “Very Much Improved”, 2 = “Much Improved”, 3 = “Minimally Improved”, 4 = “No Change”, 5 = “Minimally Worse”, 6 = “Much Worse”, 7 = “Very Much Worse”), will be presented, together with the odds ratio, associated 90% CI based on profile likelihood and 2-sided p-value based on likelihood ratio test for ASP8062 vs placebo. The cumulative logit link will be used to specify the proportional odds model in SAS.

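### SAP carries a baseline PGIC forward for subjects stopping for lack of efficacy or AEs, but PGIC has no baseline; the protocol assigns 'No Change'

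*SAP*

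**What the plan says.** **SAP.** Table 19 has a row for "Overall subject improvement assessed by PGIC at Week 2, Week 4 and Week 8" with mBOCF in the imputation column, the FAS as analysis set and a proportional odds model. The text of Section 7.4.2 repeats this: "Overall subject improvement assessed by PGIC at Week 2, Week 4 and Week 8 where mBOCF will be used for subjects with missing data". Footnote c, attached to that row, supplies the definition: "mBOCF is defined as imputation by baseline observation carried forward for subjects who discontinue due to lack of efficacy or AEs". Everyone else with a gap gets LOCF, at whichever time point is being analysed. A second PGIC analysis is also planned: "Overall subject improvement assessed by PGIC at Week 2 and Week 4 where LOCF will be used for subjects with missing data".

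**Protocol.** Section 7.4.2 covers the same analysis at Weeks 2, 4 and 8 but fills the gaps differently: "using imputation of 'No Change' for subjects who discontinue due to lack of efficacy or AEs". Everyone else with a gap gets LOCF, which the sentence words for Week 8.

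**The instrument.** SAP 6.1.2 describes PGIC as a 7-point rating of the subject's fibromyalgia compared with baseline. Protocol 5.3.1.4 and the questionnaire table in Appendix 12.6 place the first PGIC at Week 2 (Visit 4), with none at randomization. SAP 6.1 defines baseline for the tablet questionnaires and visibly names FIQR, PGIS and HADS, not PGIC; two names in that list are blacked out.

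**The concern.** A baseline-carried-forward rule needs a baseline observation. PGIC has none by construction, because the question only makes sense after treatment has started. So for subjects who stop because of lack of efficacy or an adverse event, the SAP's rule for the main analysis of a listed secondary endpoint gives no value.

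The protocol does give one. Its Non-Substantial Amendment 2 (item 4) states why the PGIC text was changed: a baseline assessment is not appropriate for this instrument. The SAP thus still carries the rule that the protocol has replaced.

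At stake is which subjects are in the model and with what value. If the conflict is left open until the data are unblinded, the choice could be made with the result in view.

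**Working it through.** **1. The passages side by side**

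| Item | SAP 7.4.2, Table 19, footnote c | Protocol 7.4.2 |
|---|---|---|
| Stopped for lack of efficacy or AE | baseline PGIC carried forward | category 4, 'No Change' |
| Missing for other reasons | LOCF at the time point analysed | LOCF, worded for Week 8 |
| Date | version 2.0, 19 April 2018 | version 1.2, 14 August 2017 |

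The SAP is about eight months later. Its revision history records the baseline-by-time correction to the MMRM, which also appears in the protocol amendment. It shows no legible entry changing PGIC at Weeks 2, 4 or 8. The one legible entry on PGIC imputation concerns EOT.

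**2. Two ways the SAP could be programmed**

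(a) No baseline record is found, the value stays missing, and the subject leaves the model. (b) A return to baseline is coded as category 4, which matches the protocol.

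**3. Size of the difference (illustration)**

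The plan states no figure to reproduce here. The only input from the documents is 89 randomized per arm; the rest is assumed.

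- Placebo completers, categories 1 to 7: A = (0.05, 0.15, 0.25, 0.35, 0.10, 0.07, 0.03) or B = (0.10, 0.25, 0.25, 0.25, 0.08, 0.05, 0.02).
- ASP8062 completers: cumulative odds multiplied by 1.80. For A, categories 1-3 have placebo odds 0.45/0.55 = 0.818; times 1.80 this is 1.473, so the cumulative proportion is 1.473/2.473 = 0.596. Categories 1-4: 0.80/0.20 × 1.80 = 7.20, so 7.20/8.20 = 0.878.
- Reading (a): completers only, so the odds ratio is 1.80 by construction.
- Reading (b): with dropout proportion d, completer proportions are multiplied by (1 − d) and d is added to category 4. One proportional odds model is fitted by maximum likelihood to the expected counts.

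Hand check for A at 10% (ASP8062) and 5% (placebo):

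- Cut after category 3: ASP8062 0.90 × 0.596 = 0.536, placebo 0.95 × 0.45 = 0.4275. Odds ratio = (0.536/0.464)/(0.4275/0.5725) = 1.55.
- Cut after category 4: ASP8062 0.90 × 0.878 + 0.10 = 0.890, placebo 0.95 × 0.80 + 0.05 = 0.81. Odds ratio = (0.890/0.110)/(0.81/0.19) = 1.90.

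The fitted common odds ratio, 1.65, lies between these.

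| Dropout ASP8062 / placebo | Excluded | 'No Change', A | 'No Change', B |
|---|---|---|---|
| 5% / 5% | 1.80 | 1.77 | 1.75 |
| 10% / 10% | 1.80 | 1.73 | 1.70 |
| 10% / 5% | 1.80 | 1.65 | 1.58 |
| 5% / 10% | 1.80 | 1.86 | 1.89 |

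Of 89 subjects, 5% is about 4.5 and 10% about 9.

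**The case against.** The best defence is that the mismatch is only loose wording. The SAP says mBOCF will be applied to missing PGIC, so it intends to give these subjects a value. On a scale of change from baseline, returning to baseline naturally means category 4. The protocol called its own edit a clarification, and the SAP describes itself as elaborating the protocol. An analyst who reads it this way gets the protocol's result. This stands as a plausible reading, so exclusion cannot be called the certain outcome. It does not remove the defect, because the SAP nowhere states that code.

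Some revision-history rows are blacked out and the PGIC window table cannot be read, so an explanation could sit there. The operative text in Table 19, its footnote and Section 7.4.2 is fully legible, however.

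A reader might also infer more than the documents support:

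- *That most early discontinuers lose their Week 8 PGIC.* No discontinuation timing is given, and the Week 8 window visible for HADS cannot be assumed for PGIC.
- *That the SAP text costs power.* In the illustration 'No Change' lowers the odds ratio when dropout is higher on ASP8062 and raises it when dropout is higher on placebo. Any loss would come from the protocol's rule, so it does not measure harm from the SAP wording.
- *That LOCF at Week 2 is an error.* No PGIC precedes Week 2, so LOCF simply leaves the observed data there. Both documents plan that analysis.
- *That LOCF scope is unresolved.* The protocol's wording names Week 8, but footnote c already sets LOCF for each time point.

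**Conclusion.** The SAP rule is wrong as written for one part of the main analysis of a secondary endpoint. It carries forward a value that does not exist, and it departs from the current protocol without a visible reason. This rests on the text alone and needs no assumption.

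The numerical consequence is conditional. If the SAP is programmed as category 4, nothing changes. If these subjects are dropped, the odds ratio differs from the protocol's version by 0.03-0.05 at 5% dropout in both arms. It differs by 0.15-0.22 at 10% versus 5%, and by 0.06-0.09 in the other direction at 5% versus 10%. The completer odds ratio, both PGIC distributions and all dropout rates behind these figures are assumed. The primary endpoint is not affected.

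**What to change.** Before unblinding, remove mBOCF and the footnote c marker from the PGIC row of SAP Table 19, and make the same change in the Section 7.4.2 text. Add a PGIC-specific footnote: category 4 ('No Change') for subjects who stop because of lack of efficacy or adverse events, and LOCF for values missing for other reasons. Record the change in the SAP revision history.

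Optional wording: say that LOCF applies at each analysed time point, and that Week 2 values missing for other reasons stay missing because nothing precedes them.

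The cost is SAP wording only. The 'No Change' rule is already in the protocol, so it needs no amendment and no new data. A one-line protocol clarification of LOCF scope could be added but is not essential.

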### 7.4.3

*Table continued on next page*

*Table continued on next page*

This figure illustrates a 2D convolutional neural network architecture. It consists of three layers: an input layer with 32 channels, a hidden layer with 16 channels, and an output layer with 1 channel. The input layer is represented by a 4x8 grid of black and white bars. The hidden layer is represented by a 4x4 grid of black and white bars. The output layer is represented by a single black bar. The grid shows the receptive fields and weights of the neurons in the hidden layer, with each neuron in the hidden layer receiving input from a specific subset of neurons in the input layer. The weights are represented by the black and white bars in the grid, where black indicates a weight of 1 and white indicates a weight of 0.

This figure displays a 10x10 grid of black and white bars, representing a 2D convolutional feature map. The bars are arranged in a grid pattern, with varying widths and heights. The grid is bounded by a thick black border. The bars are primarily black, with white bars interspersed, indicating the presence of data or a specific feature in that position. The overall pattern is a dense, irregular grid of bars.

The figure displays a 10x10 grid of black and white bars, representing a 2D convolutional feature map. The bars are arranged in a grid pattern, with varying widths and heights. The grid is bounded by a thick black border. The bars are primarily black, with white bars appearing in the following positions: (1,1), (1,3), (1,5), (1,7), (1,9), (2,2), (2,4), (2,6), (2,8), (2,10), (3,1), (3,3), (3,5), (3,7), (3,9), (4,2), (4,4), (4,6), (4,8), (4,10), (5,1), (5,3), (5,5), (5,7), (5,9), (6,2), (6,4), (6,6), (6,8), (6,10), (7,1), (7,3), (7,5), (7,7), (7,9), (8,2), (8,4), (8,6), (8,8), (8,10), (9,1), (9,3), (9,5), (9,7), (9,9), and (10,1), (10,3), (10,5), (10,7), (10,9).

The image consists of a series of horizontal bands. The majority of the bands are black, with white horizontal segments of varying lengths and positions. These white segments are irregular and do not form a continuous line. The image is set against a solid black background. The overall effect is a high-contrast, binary-like representation of a signal or data, possibly a spectrogram or a processed image of a specific type of signal.

#### **7.4.4 Analysis of Other Variables**

Not applicable.

### **7.5 Analysis of Safety**

All analysis of safety will be presented by treatment group for SAF, unless specified otherwise. No hypothesis testing will be performed comparing treatment groups for any safety parameters.

#### **7.5.1 Adverse Events**

Summaries and listings of serious adverse events (SAEs) and serious TEAEs include SAEs upgraded by the sponsor based on review of the Sponsor's list of Always Serious terms if any upgrade was done.

Duration of AE will be included in all listings and is calculated as described in Section 6.2.1

The coding dictionary for this study will be MedDRA version 20.0. It will be used to summarize AEs by SOC and PT. Standardized MedDRA query (SMQs) will also be used to identify AEs of interest as described in Section 7.5.2

##### **7.5.1.1 Adverse Events Prior to First Dose**

The number and percentage of subjects with AEs prior to first dose, as classified by SOC and PT will be summarized for each treatment group.

##### **7.5.1.2 Treatment Emergent Adverse Events**

An overview table will include the following details:

- Number of TEAEs,
- Number and percentage of subjects with TEAEs,
- Number of drug related TEAEs,
- Number and percentage of subjects with drug related TEAEs,
- Number of serious TEAEs,
- Number and percentage of subjects with serious TEAEs,
- Number of drug related serious TEAEs,
- Number and percentage of subjects with drug related serious TEAEs,
- Number of TEAEs leading to permanent discontinuation of study drug,
- Number and percentage of subjects with TEAEs leading to permanent discontinuation of study drug,

- Number of deaths,
- Number of drug abuse related TEAEs, and
- Number of drug withdrawal related TEAEs.

The above summary will be repeated for TEAEs (treatment period) and TEAEs (follow-up period).

### **7.5.1.3 Treatment Emergent Adverse Events by SOC and/or PT**

The number and percentage of subjects with TEAEs, as classified by SOC and PT will be summarized for each treatment group. Summaries will be provided for:

- TEAEs
- TEAEs (treatment period) and TEAEs (follow-up period),
- Drug related TEAEs,
- Serious TEAEs (including number of events),
- Drug related serious TEAEs (including number of events),
- TEAEs leading to permanent discontinuation of study drug,
- Drug related TEAEs leading to permanent discontinuation of study drug,
- TEAEs leading to death (including number of events)
- Drug related TEAEs leading to death (including number of events),
- TEAEs excluding serious adverse events that equal to or exceed a threshold of 5% in any treatment group.

The number and percentage of subjects with TEAEs, as classified by PT only, will be summarized for each treatment group in decreasing order of frequency within the ASP8062 treatment group.

The number and percentage of subjects with TEAEs (including number of events), as classified by SOC and PT will also be summarized by severity to study drug. In the subject count, if a subject has multiple TEAEs with the same SOC or PT, but with differing severity, then the subject will be counted only once with the worst severity. If any of the severity values are missing then the subject will be counted only once with worst severity, i.e. severe. In the adverse event count, the adverse events will be presented in each category they were classified to.

Drug related TEAEs will be presented in a similar way by severity only. When assessing severity for drug-related TEAEs as reported by the investigator, only drug-related TEAEs will be used in the analysis and the worst grade for severity will be chosen as described above.

### **7.5.2 Adverse Events of Interest**

The number and percent of subjects who have a TEAE within the Drug abuse, dependence and withdrawal SMQ (MedDRA 20.0) will be summarized by treatment group.

### **Drug abuse related TEAEs**

The number and percent of subjects who have a TEAE within the Drug abuse and dependence SMQ (MedDRA 20.0) during the treatment period and follow-up period, as classified by SOC and PT will be summarized by treatment group.

In addition, the number and percent of subjects who have Drug abuse related TEAEs during the treatment period and follow-up period, as defined in Section 10.1 Appendix 1: Drug Abuse Related Adverse Events, as classified by PT and lowest level term will be summarized by treatment group.

### **Drug withdrawal related TEAEs**

The number and percent of subjects who have a TEAE within the Drug withdrawal SMQ (MedDRA 20.0) during the treatment period and follow-up period, as classified by SOC and PT will be summarized by treatment group.

In addition, the number and percent of subjects who have withdrawal related TEAEs during the treatment period and follow-up period, as defined in Section 10.2 Appendix 2: Drug Withdrawal Related Adverse Events, as classified by SOC and PT will be summarized by treatment group.

#### **7.5.3 Clinical Laboratory Evaluation**

The baseline visit is the last measurement taken prior to first dose of study drug.

Quantitative clinical laboratory variables, i.e., hematology & coagulation, and biochemistry will be summarized using mean, SD, minimum, maximum and median for each treatment group at each visit. Additionally, a within-subject change will be calculated as the post-baseline measurement minus the baseline measurement and summarized in the same way. Each laboratory result will be classified as low (L), normal (N), or high (H) at each visit according to the laboratory supplied reference ranges.

The number and percentage of subjects below and above the reference range will be summarized for each treatment group at each visit.

For hematology and biochemistry, two types of shift tables will be presented for each treatment group:

- Shift tables of reference range changes from baseline to post-baseline value at each specified time point (low, normal, high), and
- Summary shifts of reference range changes from baseline to post-baseline value at each specified time point (shift from normal or high to low, shift from normal or low to high, categorized increase [shift from low to normal, low to high or from normal to high], categorized no change [value stays in the same reference range], categorized decrease [shift from high to normal, high to low or from normal to low]).

The following list of parameters will be summarized using descriptive statistics and for the shift table.

